1. INTRODUCTION

Background Information

DBI-001 is a topical live bacterial product containing (a strain isolated from humans,). This product is being developed as a topical probiotic for the treatment of diseases of the skin. (a strain isolated from humans,), and is an aerobic Gram-negative bacterium commonly found in the soil, water, vegetables and grains from the human food chain (Asakura et al. 2016; DR001 2019; DR002 2019) and on the skin of healthy humans (DR001 2019; DR002 2019). The strain of is a strain that DermBiont isolated from the skin of a healthy young adult. Based on c DNA sequencing, this strain has no known virulence factors nor genes that would indicate antimicrobial resistance. In vitro, the strain has been shown to inhibit the growth of *S. aureus* and dermatophytes. This strain is sensitive to commonly used antibiotics.

The human epithelial surfaces of the skin, gut, genital tract, and respiratory tract are at the interface with the outside world. These areas have long been known to be inhabited by microorganisms previously referred to as "the normal flora" which, for the most part, was not thought to contribute to health or disease. In recent years, enabled by the availability of DNA sequencing, what had been called the normal flora is now called the microbiome. DNA sequencing is able to detect the many organisms that are either difficult or impossible to grow using routine culturing techniques. A normal microbiome can contribute to health while an abnormal microbiome, a dysbiosis, can be associated with disease.

Atopic dermatitis (AD) is a common skin disease that affects a large proportion of the adult and pediatric population worldwide. *S. aureus* presence in the cutaneous microbiome of AD patients has been directly correlated to disease severity (Blazewicz et al. 2017; Hepburn et al. 2017). In the case of *S. aureus* and AD, it now appears this is not an "infection" in the traditional sense, but rather a dysbiosis characterized by decreased overall diversity of organisms and a high abundance of *S. aureus*. It has been hypothesized that in subjects without AD, the commensal bacteria in the microbiome contribute to host defense by producing metabolites that can control the abundance of *S. aureus*. The dysbiosis seen in AD may be functionally important because of a loss of these protective strains as well as the AD patient's deficiency in host produced antimicrobial peptides. Several different bacterial species on healthy human skin produce anti–*S. aureus* activity and bacteria with this activity were far less frequent on the skin of AD patients. The application of antimicrobial Coagulase Negative Staphylococci (CoNS) strains to animal or human skin greatly reduced *S. aureus* abundance. Together, these observations show that specific bacteria within the human skin microbiome defend against an overabundance of *S. aureus* (Nakatsuji et al. 2017; Williams and Gallo 2017).

DermBiont

Application of to the skin of amphibians has been shown to treat and prevent the acquisition of a lethal cutaneous fungal infection. (Harris et al. 2009). The exact mechanism by which inhibits the growth of bacteria, fungi and other microorganisms is not yet known. It is known that produces some metabolites that have antimicrobial activity. These compounds are

The use of topical live bacterial products to treat skin diseases is a new and rapidly advancing therapeutic approach. To date, at least three live bacterial products have been studied in the clinic. An ammonia oxidizing bacterium has been used in Phase 2 trials to treat acne at a dose of 10⁹ CFUs/ml (US9738870B2 2017). In addition, a coagulase-negative *Staphylococcus* strain at a dose of 10⁷CFUs/ml (Williams and Gallo 2017) has been used in atopic dermatitis patients, and a strain of *P. acne* has been applied to the face of acne patients at a dose of 10⁸CFUs/ml (Naked_Biome:NCT03450369 2018). In addition, the sponsor has completed clinical trials with DBI001 in patients with AD (DBI-CSR-203) and T. pedis (DBI-CSR-201, DBI-CSR-204).

The Sponsor believes that it is possible that the application of DBI-001 to the skin of patients with AD will decrease the abundance of *S. aureus* resulting in an improvement in the signs and symptoms of AD. This therapeutic approach would have the potential to decrease the use of oral and topical antibiotics.

1.2 Rationale

In-vitro has been shown to significantly inhibit the growth of *S. aureus* (DR005 2019) most frequently associated with AD. Application of to the skin of amphibians has been shown to be able to treat and prevent the acquisition of a lethal cutaneous fungal infection. (Harris et al. 2009). In a previous small pilot clinical trial, a single application of DBI001 was well tolerated and resulted in the reduction in the abundance of *S. aureus* and improvement in the signs and symptoms of AD, most noticeable pruritis (DBI-CSR-203). In a clinical trial of subjects with T. pedis 28 daily applications of DBI001 to the entire foot was well tolerated, decreased the abundance of T. rubrum, and improved the signs and symptoms of T. pedis. (DBI-CSR-201, DBI-CSR-204) Based on these observations, topical application of the probiotic has the potential to be a novel approach to the treatment of AD.

POTENTIAL RISKS AND BENEFITS

Potential Risks

Despite the fact that is found in the cutaneous microbiome of some people as well as in the human food chain, it is possible that application of could result in a worsening of the AD, impetigo, folliculitis, or cellulitis. It is possible that could be an opportunistic pathogen in severely immune compromised subjects. PBS solution will be used to collect samples and it could cause a local irritant reaction

As detailed in the Investigator's Brochure, if worsening of the AD, impetigo, or folliculitis or cellulitis were to occur, is susceptible to commonly used topical and oral antimicrobials and antibiotics.

Potential Benefits

It is possible that daily applications of could result in improvement in the subject's AD. Such a treatment also has the potential to decrease the use of oral and topical antibiotics.

3. STUDY OBJECTIVES AND PURPOSE

The purpose of the study is to evaluate the effect of 27 daily applications of DBI-001 on the signs and symptoms of active AD, and the safety and tolerability of DBI-001 in subjects with active AD. Secondly, to see the effect of this treatment on the abundance of *S. aureus*. Thirdly to evaluate the presence or persistence of \swarrow and the impact on the overall microbiome following once daily application of DBI-001 for 4 weeks.

STUDY DESIGN AND ENDPOINTS

Description of the Study Design

This is a randomized, observer blinded, Aqueous Gel-controlled, once daily application for 27 days within-subject, bilateral comparison trial examining the effect of DBI-001 Gel vs. Aqueous Gel. Approximately 20 subjects will be enrolled. Women of childbearing potential will be tested for pregnancy with urine pregnancy test. Women who are pregnant or who have a positive pregnancy test will be excluded from the study. At each investigative site there will be two types of investigators: treating investigators and evaluating or observing investigators. The treating investigator(s), or delegate(s), will apply the treatments and be unblinded to treatment assignment.

DermBiont

The observing or evaluating investigator(s) will be blinded to treatment assignment and perform all clinical evaluations.

Subjects meeting the inclusion/exclusion criteria will be enrolled into the study. Each subject's comparable anatomically symmetrical, bilateral treatment sites will be randomly assigned to be treated with either DBI-001 or the Aqueous Gel control. Treatments will be applied in the clinic by a treating investigator, or designee. On weekdays at home, the subjects, or LAR, will apply under the supervision (by telemed) of a treating investigator, or delegate(s), and unsupervised (no telemed visit) on weekends. Clinical evaluations will be made by a blinded-to-treatment evaluating investigator who will grade the severity of signs and symptoms of AD (erythema, pruritus, exudation, excoriation and lichenification) to calculate the ADSI score and local tolerability, which will also include assessment of the severity of pain, burning, or stinging as reported by subjects. Samples for microbiology will be tested by qPCR for the presence and abundance of and *S. aureus*, 16s and/or whole genome sequencing will be used to characterize the entire microbiome.

After Screening, study visits will occur at Day 1 Baseline (may be combined with Screening), Days 7 (\pm 2), 14 (\pm 2), 21 (\pm 2), 28 (\pm 2), 35 (\pm 4), and 42 (\pm 4). At each study visit, the following procedures will be conducted: clinical assessment of the severity of the signs and symptoms of AD (erythema, pruritus, exudation, excoriation and lichenification) and the severity of local tolerability (pain, burning, or stinging) as reported by subjects in addition to erythema, pruritus, exudation, excoriation, and lichenification.

Study Endpoints

4.2.1 Primary Endpoint

The hypothesis of this trial related to clinical effect is that 4 weeks of daily dosing with DBI-001 will improve the signs and symptoms of AD in comparison of sites treated with DBI-001 DP or Aqueous Gel on the following:

- Change from baseline in ADSI score at days 7 (±2), 14 (±2), 21 (±2), 28 (±2), 35 (±4), and 42 (±4).
- Change from baseline in individual signs and symptoms of AD (components of ADSI score) at days 7 (±2), 14 (±2), 21 (±2), 28 (±2) 35 (±4), and 42 (±2).

4.2.2 Secondary Endpoints

In the *S. aureus* MITT population, comparison of sites treated with DBI-001 or Aqueous Gel on the following microbial metrics:

- Change from baseline in abundance of *S. aureus* based on molecular diagnostic qPCR and CFU counts on samples obtained from treatment sites at days 7, 14, 21, 28, 35, and 42.
- Abundance of based on qPCR and CFU counts.
- Changes in the abundance and diversity of the microbiome as determined by 16s and/or whole genome sequencing.
- The proportion of subjects with a greater decrease in ADSI for the DBI-001-treated site than the Aqueous Gel-treated site.
- Change from baseline in signs and symptoms of local tolerability (pruritus, erythema, exudation, excoriation, and lichenification as well as pain, burning, or stinging) for the DBI-001-treated lesion and the Aqueous Gel-treated lesion.

INVESTIGATIONAL PRODUCT (IP)

Investigational Product and Aqueous Gel (Test Articles)

Test articles	Doses per Subject
1mL vial contains DBI-001 Gel with 10 ⁷ -10 ⁹ CFU / mL of	27 doses (once daily for 4 weeks)

ELIGIBILTY CRITERIA

Inclusion Criteria

Subjects must meet all of the following criteria to be included in the study:

1. Ability to understand, agree to, and sign the study Informed Consent. If the subject is unable to provide consent for him/herself, the subject's legally authorized representative may provide written consent.

2. A signed Health Information Portability and Accountability Act (HIPAA) authorization form which permits the use and disclosure of subject's individually identifiable health information.

3. Male or Female Subjects of any race 12-65 years of age.

4. Physician diagnosed clinically stable AD according to the criteria of Hanifin and Rajka with comparable anatomically symmetrical, bilateral target lesions (Hanifin and Rajka 1980). Each lesion must have an Atopic Dermatitis Severity Index (ADSI) score of ≥ 6 . It will be in the

opinion of the Investigator based on subject's medical history whether the lesions are clinically stable.

5. Female subjects of child-bearing potential must use at least one method of birth control that results in a low failure rate (i.e., less than 3 % per year) when used consistently and correctly such as implants, injectables, combined oral contraceptives, some intrauterine devices (IUDs), sexual abstinence or vasectomized partner for the duration of study participation.

6. Technical ability and willingness to self-apply, or LAR to apply, test articles during telemed visits with the study staff.

7. Willingness to discontinue use of systemic AD treatments and topical treatments to the target areas for the duration of the study unless specifically permitted by the Investigator.

8. Willingness to comply with test site restriction for 12 hours prior to all office visits including the Baseline visit and for 12 hours after each treatment application. These treatment site restrictions include:

a. No washing of test sites with any cleansers or soaps. Water passing over the areas during showering is acceptable.

b. No rubbing the test sites with a washcloth, towel, luffas. Pat dry after showering is acceptable.

c. No recreational activities in chlorinated or chemically treated water such as swimming pools, hot tubs, and spas.

d. No tight or form fitting clothing covering the treatment areas.

e. No sunbathing or use of suntan parlors or tanning beds.

f. If participating in physical activities resulting in heavy perspiration only pat dry test site areas with towel if needed.

g. Any activity that in the opinion of the investigator might alter the quality of the samples collected or risk removal of the test article.

9. Willingness to undergo the following washout periods:

a. Washout of 2 weeks prior to the Baseline visit for topical treatments used on the two treatment target sites, including but not limited to: antibacterial products, anti-inflammatories (e.g., corticosteroids, tacrolimus, Pimecrolimus). Other than the two treatment sites, topical medications may be used before/during the duration of the study. Subjects will be provided 1% hydrocortisone for treating non-target areas during the trial.

b. Washout of 4 weeks prior to the Baseline visit for systemic treatments for AD, including but not limited to corticosteroids (oral or intramuscular injections), systemic immunomodulators or immunosuppressors (e.g., methotrexate, cyclosporine, hydroxychloroquine), antibiotics (oral or injected, if required to treat a medical condition short duration of oral antibiotics (≤ 10 days) are permitted after randomization) c. Washout of 2 weeks prior to the Baseline visit for bleach baths.

d. Washout of 2 weeks prior to the Baseline visit for phototherapy.

10. No history of allergy to at least two of the following classes of antibiotics:

Cephalosporins, Quinolones, Tetracyclinea, Aminoglycosides Macrolides, Carbapenems and Lipopeptides.

11. Willingness to allow digital photos of treatment areas to be taken and stored.

Exclusion Criteria

The following are the exclusion criteria that will exclude subjects from enrolling into the trial:

- 1. Women who are pregnant, planning a pregnancy, breastfeeding or have a positive pregnancy test at screening.
- 2. Any dermatological conditions that could interfere with clinical evaluations or any disease state or physical condition which might expose the subject to an unacceptable risk by study participation.
- 3. Any underlying disease(s) or other dermatological conditions that require the use of exclusionary topical or systemic therapy.
- 4. Spontaneously improving or rapidly deteriorating dermatitis anywhere on the body.
- 5. Netherton's syndrome or other genetic dermatoses that result in defective epidermal barrier function.
- 6. Treatment of any type of cancer within the last 6 months other than cutaneous basal cell carcinoma.
- 7. History of any significant internal disease (which contraindicates use of live microbiome e.g. leukemia, liver failure, cardiovascular disease).
- 8. Subjects who are known to be allergic to any of the test product(s) or any components in the test product(s) or have a history of hypersensitivity or allergic reactions to any of the study preparations as described in the Investigator's Brochure.
- 9. AIDS or AIDS related complex by medical history.
- 10. Known or suspected immune suppressive medications or diseases or any condition that in the opinion of the investigator would increase the subject's susceptibility to opportunistic infections.
- 11. Treatment with systemic immune modulating or anti-inflammatory biologics agents within 16 weeks of Baseline Visit.
- 12. Poorly controlled diabetes mellitus Type I or II by medical history.

- 13. Peripheral vascular disease based on medical history.
- 14. Any subject not able to meet the study attendance and telemed visit requirements.
- 15. Participants with a history of psychiatric disease or history of alcohol or drug abuse that would interfere with the ability to comply with the study protocol.
- 16. Subjects who have participated in any other trial of an investigational drug or device within 30 days prior to enrollment or participation in a research study concurrent with this study.

Recruitment and Retention

Subjects will be recruited from the Investigator's clinical dermatology practice. Subjects may also be recruited through the use of recruitment material(s) approved by the study IRB or Ethics Committee.

Withdrawal or Termination

6.4.1 Subject Withdrawal

Participation in the study is strictly voluntary. A subject has the right to withdraw from the study at any time for any reason and is under no obligation to disclose the reason. If a subject withdraws, the Investigator and Sponsor are to be informed immediately and the withdrawal documented accordingly. Subjects may be replaced at the discretion of the Investigator and/or Sponsor.

The Investigator has the right to terminate participation of a subject at any time for any of the following:

- Use of non-permitted concomitant medication
- Lack of subject compliance
- Protocol violation
- Disease progression
- Any perceived safety risks

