Each enrolled subject will be randomized to a test article kit number containing two different vials of test articles for each scheduled application. Each kit will contain vials labelled with "Right" or "Left", indicating the treatment side to apply onto. Treatment compliance will be monitored by recording all missed doses in source documentation and the CRF.

DATA ANALYSIS AND STATISTICAL CONSIDERATION.

General Statistical Considerations

All statistical processing will be performed using Statistical Analysis System (SAS®) unless otherwise stated. No interim analyses are planned. Except where noted, all statistical tests will be two-sided and will be performed at the 0.05 level of significance. P-values will be provided primarily for exploratory purposes.

Descriptive statistics will be used to provide an overview of the efficacy and safety results. For categorical parameters, the number and percentage of subjects in each category will be presented. For continuous parameters, descriptive statistics will include the number of subjects, mean, and standard deviation, median, minimum, and maximum. Appropriate inferential statistics will be used for the primary and secondary efficacy variables in an exploratory manner.

Linear interpolation of efficacy variables will be performed using observed data that precedes and follows the off-schedule visit, if present. The last observation will be carried forward if all the data subsequent to the off-schedule value is missing.

No adjustments will be made for multiplicity.

DermBiont

The number of subjects in each analysis set will be summarized. Reasons for study withdrawal will be summarized using frequencies and percentages by treatment group.

Reported AEs, medical history terms and prior and concomitant procedures and therapies will be classified on the basis of the f Medical Dictionary for Regulatory Activities (MedDRA) terminology. Prior and concomitant medications will be classified on the basis of the World Health Organization Drug Dictionary (WHO-DDE) terminology.

A statistical analysis plan (SAP), describing all statistical analyses will be provided as a separate document. The SAP will be finalized prior to unblinding of the study treatments.

Analysis of Efficacy Data for Objectives

7.2.1 Primary Efficacy:

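### Section 6.4.1 ends participation, not just dosing, on grounds that include undefined disease progression, requires no later assessments and does not mask the decision, so Day 28 to 42 paired differences can be lost in an outcome-dependent way

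*Combined protocol and SAP*

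**What the plan says.** Section 6.4.1 (Subject Withdrawal) says: "The Investigator has the right to terminate participation of a subject at any time for any of the following". Five grounds follow: use of a non-permitted medication, "Lack of subject compliance", "Protocol violation", "Disease progression" and perceived safety risk. None has a definition or threshold. For progression, the section does not say which site counts or what change in ADSI is meant. The same section adds: "Subjects may be replaced at the discretion of the Investigator and/or Sponsor". That sentence closes the paragraph on withdrawal by the subject, sets no cap, and does not say whether it also covers termination by the investigator.

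On roles, Description of the Study Design says: "At each investigative site there will be two types of investigators: treating investigators and evaluating or observing investigators". The treating investigators or their delegates "will apply the treatments and be unblinded to treatment assignment", while the evaluating investigators are blinded and make all clinical evaluations. Section 6.4.1 does not say which type may terminate.

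On the data of terminated subjects:

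- Section 7.4 puts everyone randomized and dispensed product in the ITT set.
- Section 7.2.1 names no analysis population for the primary ADSI test.
- General Statistical Considerations says: "The last observation will be carried forward if all the data subsequent to the off-schedule value is missing". This is worded for off-schedule visits.
- The section on case report form completion asks only that the form be filled in as far as possible for terminated subjects.
- No section requires visits after termination.

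**The concern.** The primary comparison is within subject: the change in ADSI at the DBI-001 site minus the change at the gel site. When a subject's participation ends, both sites leave together, but what is lost is that subject's later paired difference. Progression is close to what ADSI measures, and the Potential Risks section lists worsening of AD as a possible effect of the product. A decision to terminate can therefore depend on the outcome under test. If it depends on the difference between the sites, for example because the decision-maker knows which side received DBI-001, the remaining pairs are a selected sample. Replacement restores the count but not the lost differences. With about 20 pairs, two to four terminations are 10–20% of the data.

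**Working it through.** **No figure in the plan to reproduce.** Section 7.5 bases the sample size of about 20 on clinical judgement and gives no effect size, SD, power or dropout rate. For orientation, with a two-sided 5% test, 80% power and Wilcoxon efficiency 0.955, the detectable effect is (1.960 + 0.842)/√(0.955·n) SDs of the paired difference. That is 0.64 for 20 pairs and 0.72 for 16. This is the price in precision of losing 4 pairs, even with no bias.

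**Model for bias.** From the plan: 20 pairs and a two-sided signed-rank test at 0.05. Assumed: no true effect; an early and a Day 28 paired difference, both standard normal, with correlation r = 0.7; participation ended for the k subjects whose early difference is most unfavourable to DBI-001, k = 2 or 4. This is deliberately a one-sided scenario.

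The expected four largest of 20 standard normal values are 1.87, 1.41, 1.13 and 0.92. Their sum S is 3.27 for k = 2 and 5.32 for k = 4.

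- Dropped: the shift towards DBI-001 is r·S/(20 − k). This is 0.7 × 3.27/18 = 0.13 SD and 0.7 × 5.32/16 = 0.23 SD.
- Dropped and replaced under the same selection: the shift is r·φ(z)/(1 − p), where p is the share removed and z the matching normal cut-off. This is 0.7 × 0.1755/0.9 = 0.14 SD at 10% and 0.7 × 0.2800/0.8 = 0.25 SD at 20%.
- Early value carried forward: each removed pair contributes its early value rather than a Day 28 value that has partly regressed to the mean. The shift against DBI-001 is (1 − r)·S/20. This is 0.3 × 3.27/20 = 0.05 SD and 0.3 × 5.32/20 = 0.08 SD.
- Follow-up continued, or removal symmetric between sides: the shift is 0.

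Simulated two-sided rejection rates (nominal 5%):

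| Handling | 2 of 20 | 4 of 20 |
|---|---|---|
| Dropped | 8–9% | 15–16% |
| Dropped and replaced | 8–9% | about 20% |
| Carried forward | about 4% | 4–5% |
| Follow-up continued | about 5% | about 5% |
| Symmetric removal, dropped | about 5% | 4–5% |

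**Second model, as a sensitivity check.** Here termination can follow once a site is at least 2 ADSI points worse than baseline at Day 7, 14 or 21. The assumptions are: SD of change 2 per site, between-site correlation 0.5, visit autocorrelation 0.6 or 0.8, and a probability of stopping of 0.5 or 1 at each visit where the criterion is met.

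- Either site can trigger (20–35% stopped): bias is about 0 and rejection about 2–3% in each direction, however the data are handled.
- Only the DBI-001 site triggers, and only when it is worse than the gel site (10–18% stopped): dropping gives a bias of 0.11–0.26 points towards DBI-001, with false findings in its favour in 3.6–6.6% of trials. Replacing gives 0.11–0.25 points and 3.9–7.0%. Continued follow-up gives 2.0–2.4%.
- Carrying forward under that trigger gives 0.10–0.29 points against DBI-001, with false findings for the gel in 3.6–7.8%. Adding both directions, total rejection runs from 4.7% to 8.3%.

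The two models agree on direction. The size varies with the assumptions.

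**The case against.** A reader might infer that the plan authorizes unblinded investigators to remove subjects. It does not say so. Section 6.4.1 is silent on role, blinded evaluators make all clinical evaluations, and section 6.6.1 asks for the same blinded grader throughout. What stands is that nothing keeps the treating investigator out of the decision, and that role applies clinic doses and, directly or through a delegate, supervises weekday doses by telemedicine.

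A reader might also infer that terminated pairs vanish and the result then favours DBI-001. The documents do not support that. Section 7.4 keeps these subjects in the ITT set, nothing says replacement removes them, and if the early value is carried forward the bias runs the other way. This limits the claim about direction but leaves a gap. The carry-forward rule is not clearly written for terminations, and section 7.2.1 names no population. The separate SAP that the protocol announces could settle the handling, but it cannot recover assessments that were never made.

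Nor is there a shown link between non-compliance or protocol violation and the side difference. Both sites are treated by the same person on the same schedule, and for treatment-site-restriction violations the protocol already records the event and continues evaluation. The case for bias rests on progression.

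Finally, a masked decision-maker cannot systematically select against the DBI-001 side, and the plan calls its p-values primarily exploratory. Both points are fair and lower the stakes. They do not argue for giving up observations that can be collected at visits already scheduled.

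**Conclusion.** The concern holds in a conditional form. Section 6.4.1 permits outcome-dependent loss of the Day 28 to 42 paired differences, and neither masks the decision nor requires the data to be collected. With removal symmetric between sides, the cost is precision only. With removal that tracks worsening at the DBI-001 site, dropping subjects biases towards DBI-001 by about 0.13 SD (8–9% rejection) with 2 of 20 removed, and by about 0.23–0.25 SD with 4 removed (15–16% if dropped, about 20% if also replaced). Carrying the early value forward biases against DBI-001 by about 0.05–0.08 SD with no overall type I inflation in that model. One setting of the second model did reach 8.3%.

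The number of terminations, the correlation and the one-sided selection are all assumptions, and the documents give no figure for any of them. The documents do not show that such selection will happen, or that the result would favour DBI-001 if it did. They do leave open both whether it can happen and which way it would act.

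**What to change.** In section 6.4.1, state that stopping test article is not leaving the study. Unless consent is withdrawn, both sites keep the scheduled evaluations and swabs to Day 42, and the observed values enter the ITT analysis.

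Have non-safety termination and replacement decisions made or documented by someone masked to side, with the reason recorded. Confirm that replaced subjects stay in the ITT set that section 7.4 already defines. Name that set for the primary test in section 7.2.1, and say how values are handled when a terminated subject still has none. Reconcile the protocol-violation ground with the instructions under Study Visits and in section 6.5.2 to record restriction violations and continue.

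The criteria for stopping dosing are left to the sponsor. The cost is protocol wording plus a few already scheduled visits for subjects who stop early. In both models, continued follow-up brings the bias to about 0 and total rejection to about 5% or slightly below.
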